Validation of Assessment of Bmi-1 on Protein and Molecular Levels in Oral Dysplasia and Squamous Cell Carcinoma: A Diagnostic study

November, 10 2017

Presented By:

[name]

I. Title:

Validation of Assessment of Bmi-1 on Protein and Molecular Levels in Oral Dysplasia and Squamous Cell Carcinoma: A Diagnostic study

II. Introduction:

Head and neck squamous cell carcinoma (HNSCC) including oral squamous cell carcinoma (OSCC) has been reported as the sixth most common cause of cancer mortality in the world and the fifth most commonly occurring cancer [1]. Thus a compelling need for investigation of the underlying molecular events associated with OSCC tumorigenesis has emerged for better understanding of such lesion. Moreover, identification of biomarkers for early detection and prediction of prognosis became of extreme importance, as it was reported that early diagnosis has been vital for effective treatment of OSCC and improved the survival rate of OSCC patients [2, 3].

OSCC may originate from malignant transformation of the normal oral mucosa, as well as from oral potentially malignant lesions (OPMLs) with different degrees of oral epithelial dysplasia (OED) [4]. The approach of a step-wise transition from OPMLs to OSCC was well-established, but it could be difficult to predict if and when an OPML would undergo full transformation and resulted in a tumor[5]. Thus, using specific molecular biomarkers able to identify OED lesions with higher potential for malignant transformation would be very beneficial[4]. Unfortunately, up to date there has been no tools available to monitor OED lesions or HNSCC patients for early stages of local recurrences or distant metastases [6].

Among the recently introduced biomarkers, B-lymphoma Moloney murine leukemia virus insertion region-1 (BMI1), a member of the polycomb group (PcG) genes, was considered to be pivotal in regulating stemness-related genes involved in maintaining the self-renewal ability of stem cells by promoting chromatin modifications. BMI1 was also known to be deregulated in various human types of cancer [7] [8] [9] [10]. Previous studies have revealed the capability of BMI1 to be used as a prognostic marker in gastric[11], esophageal[12], nasopharyngeal cancer[7], prostate[13], breast [9], cervical [14] and ovarian cancer [10], However,

the role of BMI1 in maintaining self-renewal and tumorigenicity in HNSCC or HNSCC-derived cancer stem cells (CSCs) remained to be clarified.

III. Review of literature:

HNSCC often developed within pre-neoplastic fields of genetically-altered cells with different degrees of OED. The presence of OED in OPMLs was generally accepted as one of the most reliable predictors of malignant development [15], however, histopathologic diagnosis was subjective and lacked sensitivity. No approval was reported on which dysplastic features were important in predicting progression. In addition, there was both inter- and intra-observer variation in illustrating the degree of epithelial dysplasia[5]. Thus, several studies have been administered to identify objective molecular biomarkers to diagnose and prognose OED using different types of markers such as loss of heterozygosity, DNA ploidy, telomerase activity, methylation, and gene expression analysis [5].

Despite the advances that have been made in HNSCC treatment, prognosis remained discouraging. The major cause of recurrence and metastasis, both local and distant could be attributed to the diverse architecture of this tumor that consisted of functionally heterogeneous lineages of cancer cells that harbour cancer stem cell (CSC) properties [16] [17] [18] [19]. This hypothesis has gained support in a variety of tumors in addition to cultured cancer cell lines [20] [21] [22]. These CSCs have shown to be key contributors to radio- and chemoresistance and were responsible for tumor progression and recurrence after conventional therapy [23] [24].

CSCs were defined by their extensive self-renewal, differentiation and tumor initiation properties [25]. They were considered as the actual tumor initiating subpopulation and could expand depending on its evolutionary landscape during cancer development [16]. Recent findings have suggested that the persistent survival of CSCs, might contribute to the aggression and recurrence of HNSCC [26] [27] [23, 28]. Moreover, published studies suggested a direct link between epithelial-mesenchymal transition (EMT) and the gain of CSC-like properties[29]. The EMT process was considered as a critical step in the induction of tumor metastasis and malignancy [30].

The acquisition of genetic or epigenetic predisposition to tumorigenicity by CSCs has been shown to be a cumulative process [31] that might be evident in premalignant lesions [32] [33] as well as oral epithelial tumorigenicity [34]. This increased the importance of unraveling the underlying molecular events associated with CSC population, as they could serve as early detectors of malignant potential in OED and prognosis of OSCC. Thus, the signaling pathways required for the maintenance of CSCs became candidate targets of recent investigations in this field. Currently, light was shed on **B-lymphoma Moloney murine leukemia virus insertion region-1** (BMI-1) which has been implicated in the regulation of CSCs.

BMI-1 oncogene is a member of the polycomb-group gene family and a transcriptional repressor. BMI-1 was first recognized in a B-cell lymphoma as a transcriptional repressor that was a member of the P_cG transcription factors [35]. Certain studies have revealed that BMI-1 was involved in the self-renewal, differentiation and tumor initiation of CSCs [36] [37] [25]. Nevertheless, the molecular mechanisms underlying these biological processes remained vague.

In addition, BMI-1 was known to be upregulated in various human cancer tissues and was important in the regulation of malignant transformation, proliferation, cell cycle, apoptosis and distant metastasis [38]. Actually, many studies have reported that Bmi1 was overexpressed in HNSCC cells when correlated to normal epithelium and was thought to impact cell proliferation and survival in HNSCC [39] [40] [41] [42]. **Song et al 2009.**, demonstrated that Bmi-1 mRNA and protein expression levels were found to correlate with the invasion of nasopharyngeal carcinoma [7].

In clinical specimens of HNSCC, many researchers have established that the overexpression of Bmi-1 correlated with poor overall survival [43] [39] [41]. Likewise, **He et al 2015.**, added that the expression of Bmi1 was correlated with poor overall survival and was also associated with lymph node metastasis and clinical stage.

Association of Bmi1 overexpression, and stem-like properties in tumor cells could be attributed to induction of the EMT that promoted invasion, metastasis, and poor prognosis [41]. In the same background, **Yang et al., 2010** showed that BMI1 was necessary for EMT during tumor development in head and neck cancer patients [8].

Strong evidence suggested that Bmi1 was important to invasive potential and favored to the maintenance and self-renewal of CSCs in several tumor types, including HNSCC [44] [41] [24] [45]. As a stem cell marker, Bmi1 played a key role in the functioning of endogenous stem cells and CSCs [46] [45]. Additionally, it has been found to be related to many other CSC markers such as SOX2 [47], Oct4 [48], Nanog [48], ALDH1[32], ABCG2 [2] and CD44 [49] [50]. **Seo et al., 2011** found a connection between BMI-1 and Sox2 in maintaining self-renewal and identified BMI-1 as a key mediator of Sox2 function [47].

Moreover, recent studies have revealed that Bmi-1 expression was associated not only with the development of oral cancer, but also in patients with oral leukoplakia (LP)[40], oral erythroplakia[32], and oral lichen planus[42]. Furthermore, Bmi-1 overexpression was found in LP, and increased significantly from mild to moderate and severe LP. Consistent results were reported in Kang's research, which showed that Bmi-1 overexpression was observed in preneoplastic oral mucosal tissues, including mild, moderate or severe OED [51]. **Ma L et al., 2013** suggested that Bmi1 may act as a beneficial marker for the recognition of high risk of malignant progression of OLP [42].

Wang et al., 2015 studies have indicated that silencing BMI-1 can decrease the malignant biological behavior of cancer, in addition to the self-renewal and differentiation of CSCs. Therefore, BMI-1 was hypothesized to affect the malignant biological behavior of human tumors by regulating the self-renewal and differentiation of CSCs. In conclusion, BMI-1 might represent a hopeful target for the prevention and therapy of various types of human cancer. Further understanding the molecular mechanism underlying the regulation of BMI-1 in human cancer and CSCs is of extremely huge clinical value [52].

PIRT

P→ Diagnostic validity of Bmi-1 levels in archival paraffin embedded tissue samples of oral dysplasia and squamous cell carcinoma.

I 1 → Expression of Bmi-1 protein level by immunohistochemistry in oral dysplasia and squamous cell carcinoma.

I 2 → Expression of Bmi-1 molecule at RNA level by PCR in oral dysplasia and squamous cell carcinoma.

R→ biopsy embedded in paraffin blocks.

T→oral dysplasia and squamous cell carcinoma.

IV. Research Question:

Does the expression of Bmi-1 vary from oral epithelial dysplasia to different grades of squamous cell carcinoma at protein and molecular levels? Which one of them is more sensitive and specific for Bmi-1 assessment, the protein or molecular levels?

V. Methods:

Source of data:

Convenient consecutive sampling; it will include all archived blocks in the past 5 years (2012-2017).

Study design: Prospective cohort (In vitro validation study test)

Participants:

The archival paraffin embedded tissue samples which will be included in this diagnostic study are 30 samples of oral dysplasia and squamous cell carcinoma. We will apply a convenient consecutive sampling; it will include all archived blocks in the past 5 years (2012-2017) for this validation study. Excluded are samples of sarcomas or benign tumors or any carcinoma other than squamous cell carcinoma or any other techniques rather than immunohistochemistry or PCR. Samples that fulfilled the eligibility criteria will be included consecutively (consecutive sampling) until the target sample size will be reached. Data regarding Bmi-1 antibody expression in oral dysplasia and different grades of squamous cell carcinoma will be collected prospectively from both the reference and index tests independently.

Predictors:

Biopsy embedded in paraffin blocks was selected as reference standard method to assess the expression of Bmi-1 antibody at protein and RNA levels by immunohistochemistry and PCR respectively.

FIRST , PCR ANALYSIS

According to **Borbély et al 2007** tissue blocks will be prepared as follow:

- 1-** Tissue of 30 microns will be cut from paraffin blocks using scalpel and was put in eppendorf.
- 2-** 200 ml of tissue lysis buffer (ATL) + 0.6 ml of DNAs inhibitors + 10 ml proteinase K will be added to the sample.
- 3-** Sample will be incubated at 55 °C for 20 min.
- 4-** 250 micron of ethanol will be added and the sample will be left for 5min at room temperature.
- 5-** Sample will be collected by micropipette into spin column and will be centrifuged at 8000/ rpm for 1 min.
- 6-** 500 microlitre of wash buffer 1 will be added and the spin column will be centrifuged at 8000/ rpm for 1 min.
- 7-** 500 microlitre of wash buffer 2 will be added and the spin column will be centrifuged at 8000/ rpm for 1 min.
- 8-** 500 microlitre of elusion buffer will be added and the spin column will be centrifuged at 14,000/ rpm for 3 min.
- 9-** 490 microlitre of distilled water will be added for each of DNA extracted sample.
- 10-** Spectrophotometer assessment will be done for concentration and purification of extracted nucleic acid (measurement of extracted nucleic acid 260/280 absorbance UV.

- 11- The sample will be divided into two portions in 200 ml eppendorfs.
- 12- The first portion will be added to SYBERGREEN for amplification and quantitation of Bmi-1 gene by real time PCR using APPLIED BIO SYSTEM (U S A).
- 13- The second portion will be added to SYBERGREEN for amplification and quantitation of Bmi-1 receptor gene by real time PCR using APPLIED BIO SYSTEM (U S A).

SECOND, IMMUNOHISTOCHEMISTRY

A-Reagents:

- 1- **Primary antibody** BMI-1 rabbit polyclonal antibody
- 2- **The universal immunostaining detection kit** (Dako Cytomation Envision+ Dual link system, Peroxidase (DAB+) Code K4065, Carpinteria, CA,USA).
- 3- **Buffer:** Phosphate buffer saline (PBS) of pH 7.4 (1.48 gm dibasic sodium phosphate anhydrous, 0.43 gm monobasic potassium phosphate anhydrous and 7.2 gm sodium chloride in one liter of distilled water).

B-Procedures:

- 1- **Deparaffinization:** The paraffin sections will be deparaffinized in three changes of xylene, and will be placed for 10 minutes in each change at room temperature.
The excess liquid will be drained and the slides will be transferred to alcohol, 15 minutes for each descending grades of concentrations (100%, 70% then 50%). Then the slides will be rinsed under tap water for 5 minutes.
Immersion of slides in PBS (2 changes), 5 minutes for each.
- 2- **Epitope retrieval:** Citrate Buffer Epitope Retrieval method will be used in this technique. Briefly, a steamer for water bath will be preheated with staining dish containing citrate buffer (ph 6.0) until temperature will be reached 95-100°C. Slides will be immersed in the staining dish and the lid will be loosely placed then will be incubated for 20 minutes and will turn off the steamer. The

staining dish will be placed at room temperature and will be allowed to cool for 20 minutes.

- 3- Primary antibody: sections will be incubated in rabbit anti-Bmi-1 individually for 1 hour at room temperature. Sections will be rinsed in 2 changes of washing buffer, 2 minutes each.
- 4- Serum block: sections will be incubated with normal horse serum blocking solution for 30 minutes to block non-specific binding of immunoglobulin. The best results will be obtained with dilution 1:25. Slides will be rinsed in washing buffer for 2×2 min
- 5- Peroxidase blocking: sections will be incubated in peroxidase blocking solution for 10 minutes to block endogenous peroxidase activity.
- 6- Slides will be rinsed in washing buffer 3×2 min
- 7- Secondary antibody: sections will be incubated with biotinylated horse Anti-Mouse IgG diluted in secondary antibody dilution.
- 8- Slides will be rinsed in washing buffer 3×2 min.
- 9- Chromogen/substrate: sections will be incubated in DAB peroxidase substrate solution for 5-10 min and then will be rinsed with distilled water
- 10- Slides will be counter stained with Mayer's haematoxylin solution, then will be rinsed in running tap water for 5 minutes
- 11- Slides will be dehydrated through 95% ethanol for 2 minutes, 100% ethanol for 2×3 minutes
- 12- Finally, they will be cleared in xylene for 2-3 minutes and cover slipped with permanent mounting medium.

Since BMI-1 level is measured objectively then no blinding is required.

First: Calculation of Relative Quantification (RQ) (relative expression):

After the RT-PCR will run, the data will be expressed in Cycle threshold (Ct).PCR data sheets will include Ct values of assessed gene and the house keeping (reference) gene which will be continuously expressed in the cell- (β -actin).To measure the gene expression of certain gene, -ve control sample shall be used. So target gene expression will be assessed and related to reference (internal control) gene as follows:

Finally, RQ was calculated according to the following equation:

1. ΔCt (Cycle threshold) = Ct assessed gene – Ct reference gene
2. $\Delta\Delta Ct$ = ΔCt sample – Ct control gene
3. $RQ = 2^{-(\Delta\Delta Ct)}$

Second: Image analysis:

In order to provide more précis data on Bmi-1 immunoexpression in OSCC, image analyzer will be used.

The data will be obtained using the software (SIS, Germany), which comprise a light microscope (Olympus B \times 60 Japan) capable of performing high speed digital image processing for the purpose of cell measurements. It will be calibrated automatically to convert the measurement units (pixels) produced by image analyzer program into actual micrometer units. In immunohistochemical sections, and by using the image analyzer, five specific fields showing maximum positivity of Bmi-1 expression will be used in each case; the mean of five values of each slide will be calculated and statistically will be analyzed. For each field of immunostained section, a measuring frame of area 1920000 pixels and then the area % will be calculated. The color of immunostaining will be automatically selected according to the positive control sections, converted into grey color then masked the red and white to allow automatic measurements by the computer system. Data obtained will be subjected to statistical analysis using Student-t test.

Since BMI-1 level is measured objectively then no blinding is required.

Sample size

The aim of the current study is to assess the validation of Bmi-1 detection at both protein and molecular levels in oral epithelial dysplasia and oral squamous cell carcinoma as a biomarker for early cancer detection versus biopsy embedded in paraffin blocks. We are going to apply a convenient consecutive sampling; it will include all archived blocks in the past 5 years (2012-2017) about 30 samples.

Statistical analysis methods:

Data will be analyzed using IBM SPSS advanced statistics (Statistical Package for Social Sciences), version 21 (SPSS Inc., Chicago, IL). Numerical data will be described as mean and standard deviation or median and range. Categorical data will be described as numbers and percentages. Correlation analysis will be used. Agreement between both methods will be analyzed with the use of kappa statistics.

References:

1. Nagadia, R., et al., *miRNAs in head and neck cancer revisited*. Cellular Oncology, 2013. **36**(1): p. 1-7.
2. Dalley, A.J., et al., *Expression of ABCG2 and Bmi-1 in oral potentially malignant lesions and oral squamous cell carcinoma*. Cancer medicine, 2014. **3**(2): p. 273-283.
3. Kurihara, K., et al., *Expression of BMI1 and ZEB1 in epithelial-mesenchymal transition of tongue squamous cell carcinoma*. Oncology reports, 2015. **34**(2): p. 771-778.

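### The immunohistochemistry steps contradict their own reagent list: a rabbit primary and a universal peroxidase kit are listed, but step 7 applies a biotinylated anti-mouse secondary; the serum block also comes after the primary

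*Combined protocol and SAP*

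**What the plan says.** All of this is in the Methods part of the combined protocol and SAP, under the immunohistochemistry heading (A-Reagents and B-Procedures) and the image analysis heading.

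- **Reagents.** The primary is a "BMI-1 rabbit polyclonal antibody". The detection kit is the "Dako Cytomation Envision+ Dual link system", described as universal and as a peroxidase/DAB product.
- **Step 3.** After epitope retrieval, "sections will be incubated in rabbit anti-Bmi-1 individually for 1 hour at room temperature". No block is listed before this.
- **Step 4.** Next, "sections will be incubated with normal horse serum blocking solution for 30 minutes to block non-specific binding of immunoglobulin".
- **Step 5.** Then "sections will be incubated in peroxidase blocking solution for 10 minutes to block endogenous peroxidase activity".
- **Step 7.** The secondary: "sections will be incubated with biotinylated horse Anti-Mouse IgG diluted in secondary antibody dilution".
- **Step 9.** After a rinse, "sections will be incubated in DAB peroxidase substrate solution for 5-10 min".
- **Image analysis.** The outcome is the mean percentage of stained area over five fields per slide, chosen where staining is strongest. The colour to be counted is selected automatically from positive control sections. The values go to a Student t-test. The statistical methods section adds correlation and a kappa for agreement between the two methods.

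**The concern.** The secondary in step 7 is directed at a different species from the one in which the primary was raised, and it belongs to a different detection chemistry from the kit that is listed. A laboratory following the numbered steps and one following the reagent list would not run the same assay.

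Stained area is the only immunohistochemistry measurement in the plan. It carries the protein half of the research question, which asks whether protein or molecular assessment is the more sensitive and specific. If the colour on the slide does not come from the anti-Bmi-1 antibody, the t-test compares something else, and the kappa with PCR measures agreement between Bmi-1 RNA and an unknown quantity. No analysis can repair that after the slides are stained.

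The place of the serum block is a lesser worry: it adds a route for background staining in a measurement that has little protection against it.

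**Working it through.** No arithmetic applies. The plan gives no background rate, standard deviation, positivity cut-off, power or effect size for the stain. The check is a comparison of the reagent list with the steps in order.

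**1. Species.** The primary is rabbit in the reagent list and again in step 3, so this is not a slip in one place. The step 7 secondary is anti-mouse. The documents do not say that such a reagent fails on rabbit IgG; that is general laboratory knowledge and is used here as an assumption. Under it, step 7 as written has no specific target on the slide.

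**2. Detection chemistry.** The listed kit is a peroxidase/DAB system. Step 7 uses a biotin label instead. Step 8 is a rinse and step 9 is DAB. DAB is a peroxidase substrate, but nothing listed between steps 7 and 9 brings peroxidase to the biotin. The kit could supply the enzyme, but no step names it. The sequence as written therefore lacks a link, independently of the species question.

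**3. Order of the blocks.**

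| Step | Action | Relative to primary | Relative to secondary and DAB |
|---|---|---|---|
| 3 | Rabbit primary, 1 hour | – | before |
| 4 | Horse serum block, 30 min | after | before |
| 5 | Peroxidase block, 10 min | after | before |
| 7 | Biotinylated anti-mouse secondary | after | – |
| 9 | DAB, 5–10 min | after | – |

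The serum block can still limit non-specific binding of the secondary. It cannot undo non-specific binding of a primary that has been on the section for an hour. The peroxidase block comes before any enzyme or substrate step, so it can do what it is there to do.

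**4. Safeguards against background.** Three features of the image analysis make background harder to see. Fields are picked for the strongest staining. The colour is set from positive controls only. No negative control (primary omitted) is described for the stain; the only negative control mentioned belongs to the PCR calculation.

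**The case against.** The strongest reply is that step 7 may be no more than a wording error. A universal kit is listed, and the DAB in step 9 fits it. If the kit is what the laboratory uses, and if it recognises rabbit IgG (the documents do not say), the stain may be sound. The positive control sections also help: if the secondary did not recognise the primary, those sections should fail to stain specifically, and a complete failure would probably be noticed. Both points stand. They limit the conclusion to the procedure as written; they do not remove the contradiction, and a positive control does not reveal non-specific background.

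Three stronger readings are tempting, and the documents do not support them:

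- **A reader might infer that the stained area cannot be read as Bmi-1 at all.** That follows only if step 7, and not the listed kit, is what is carried out. The text does not settle which.
- **A reader might infer that the peroxidase block is also misplaced.** It precedes both the secondary and DAB, which is enough for its stated purpose.
- **A reader might infer that background would necessarily distort the planned comparisons.** A constant amount b added to every sample leaves a difference in means unchanged, since (x + b) − (y + b) = x − y. It also leaves the standard deviation, the t statistic and the correlation unchanged. Kappa could change, but no cut-off is given from which to work out by how much. Harm to the t-test or correlation would need background that varies between samples or groups, on which the documents give no information.

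It is also fair to say that step 4 does not specify which immunoglobulin it means. Its position does not contradict its stated purpose outright; it leaves the primary uncovered.

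**Conclusion.** The contradiction is established from the text: a rabbit primary and a universal peroxidase kit on one side, a biotinylated anti-mouse secondary with no listed peroxidase conjugate on the other. Performed as written, and on the assumption that an anti-mouse reagent does not specifically detect rabbit IgG, step 7 would yield a stained area that could not be attributed to Bmi-1. The t-test and the agreement with PCR would lose their meaning.

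The size cannot be given as a number. In extent, it would affect all of the roughly 30 samples and one of the two index tests, because every slide goes through the same steps.

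The late serum block is a secondary weakness: a risk of background from the primary, made worse by the choice of fields and the lack of a negative control, but not evidence that the stain fails. The point should be settled before staining.

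**What to change.** 1. Rewrite step 7 so that it uses the listed kit, or another single system that recognises rabbit IgG, and state the step that supplies peroxidase before DAB. Make the reagent list match.
2. Move the serum block (step 4) ahead of the primary (step 3). The peroxidase block need not move.
3. Preferably, add a slide with the primary omitted to each staining batch, as a check on background alongside the positive control.

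Items 1 and 2 are changes of wording; the kit is already listed, so using it adds no new reagent to the list. Item 3 costs one slide per batch; the documents do not give the number of batches. All three need to be in place before the first slide is stained.

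### The written immunohistochemistry steps pair a rabbit primary antibody with an anti-mouse secondary and add no peroxidase label before the DAB substrate

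*Combined protocol and SAP*

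**What the plan says.** The relevant text is in V. Methods, under Immunohistochemistry.

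- **A-Reagents, item 1** gives the primary antibody as "BMI-1 rabbit polyclonal antibody".
- **A-Reagents, item 2** lists the only detection system, "The universal immunostaining detection kit", identified as a peroxidase (DAB+) product.
- **B-Procedures, step 3** repeats the host species: "sections will be incubated in rabbit anti-Bmi-1 individually for 1 hour at room temperature".
- **Step 4** is the serum block: "sections will be incubated with normal horse serum blocking solution for 30 minutes to block non-specific binding of immunoglobulin".
- **Step 5** is the peroxidase block: "sections will be incubated in peroxidase blocking solution for 10 minutes to block endogenous peroxidase activity".
- **Step 7** is the secondary antibody: "sections will be incubated with biotinylated horse Anti-Mouse IgG diluted in secondary antibody dilution".
- **Steps 6 and 8** are rinses, and **step 9** applies a DAB peroxidase substrate.

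The stain is then read by image analyser as area %, averaged over five fields per case and compared by Student's t-test. Statistical analysis methods adds a correlation analysis, with unnamed variables, and a kappa for agreement between the two methods.

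**The concern.** There are two faults: a contradiction and an omission.

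The contradiction is that the primary antibody is rabbit in both places where its host is named, yet the secondary antibody is directed at mouse IgG. That secondary is not in the reagent list, and no step applies the kit that is.

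The omission is that DAB is a peroxidase substrate, so colour needs peroxidase on the section. The secondary carries biotin. No later step adds an avidin- or streptavidin-peroxidase, or any other peroxidase-labelled reagent, and the endogenous enzyme has been blocked.

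Immunohistochemistry is the protein-level index test, and IV. Research Question asks: "Which one of them is more sensitive and specific for Bmi-1 assessment, the protein or molecular levels". A comparison of two assays depends on each assay being one that can be stated and repeated. If the written steps were followed, area % would not measure Bmi-1 protein, and whatever is computed from it would share that defect. If they are not followed, the protocol does not say what was done instead.

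**Working it through.** The plan states no figure to reproduce here; the check is a comparison of texts. The table covers every step from the primary antibody to the chromogen.

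| Step | What is applied | Stated to recognise rabbit IgG? | Supplies peroxidase? |
|---|---|---|---|
| 3 | Rabbit anti-Bmi-1 primary | (is the primary) | No |
| 4 | Normal horse serum block, then rinse | No | No |
| 5 | Peroxidase block | No | No (it blocks the endogenous enzyme) |
| 6 | Rinse | – | – |
| 7 | Biotinylated horse anti-mouse IgG | No | No (biotin label only) |
| 8 | Rinse | – | – |
| 9 | DAB peroxidase substrate | – | No (needs it) |

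**Count.** Steps 4 to 8 are 5 steps. Removing the 2 pure rinses (6 and 8) leaves 5 − 2 = 3 reagent steps (4, 5 and 7). Peroxidase-labelled: 0 of 3. Stated to recognise rabbit IgG: 0 of 3. Two of the three are blocks and would not be expected to carry a label, so the finding rests on step 7. It is the only detection step, it is aimed at another species, and it carries no stated peroxidase.

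**Could the listed kit close the gap?** It might contain a suitable reagent, but no step applies one. The reagent list calls the kit universal without saying which species it recognises.

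**Could it be a one-word slip, mouse for rabbit?** Correcting the species would still leave a biotinylated antibody followed by a rinse and DAB, with no label. The horse serum in step 4 and the horse antibody in step 7 are both absent from the reagent list, so the mismatch is wider than one word.

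**Readings affected if the steps are followed as written.** Sample size gives about 30 samples, and Image analysis gives five fields per case: 30 × 5 = 150 field readings, averaged to 30 slide means. These are maxima. Image analysis is introduced for OSCC, the 30 samples also include dysplasia, and the split is not given.

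**Analyses affected.**

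- The t-test is tied explicitly to the image data.
- The kappa is tied by its reference to both methods. Kappa needs categories, and no cut-off is given for area % or for the PCR relative quantification, so how the stain enters it is undefined.
- The correlation is tied only by inference, because its variables are not named.

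**The case against.** The best reply is that this is a drafting fault unlikely to reach the data. The protocol does name a peroxidase/DAB detection kit, and steps 5 and 9 are compatible with it, so the species conflict sits in a single line that may have been carried over from another procedure. A run with no signal would probably be noticed: the analyser colour is selected from positive control sections, and if these pass through the same steps there would be no stain to select. The outcome of a literal run also rests on general laboratory reasoning. The documents do not address cross-reaction of an anti-mouse antibody with rabbit IgG, or how complete the peroxidase block is.

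Much of this stands. It makes corrupted results less likely than an undocumented assay, it makes 150 a ceiling, and it limits firm confidence to the textual comparison. It does not resolve the contradiction. If the kit will be used, step 7 is wrong. If step 7 will be used, the reagent list is wrong and a label step is missing. Cross-reaction, even if it occurred, would still leave DAB without a stated peroxidase. Nothing elsewhere in the document settles which reading is intended.

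**Conclusion.** The concern holds and should be fixed before staining. The procedure conflicts with its own reagent list on the species of the secondary antibody and on the detection system, and it gives no source of peroxidase for the DAB reaction. As written, little or no Bmi-1-specific colour would be expected.

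The consequence depends on a fact the documents do not supply:

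- **Steps followed as written:** all the stain readings, at most about 150 from about 30 slides, and the t-test on them would not measure Bmi-1 protein. The kappa would be affected as well, and presumably the correlation.
- **Step 7 is carried-over wording:** the results may be sound, but the protein assay in a validation study is undocumented and cannot be reproduced from the protocol.

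Confidence is high for the contradiction and the missing label step. No size or direction of bias is claimed in either case.

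**What to change.** Rewrite B-Procedures steps 3 to 9 before any section is stained, so that they and A-Reagents describe one detection system.

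- **Natural option:** replace step 7 with the peroxidase detection reagent of the kit already listed, after confirming from the kit's instructions that it recognises rabbit IgG.
- **Otherwise:** name a secondary antibody directed at rabbit IgG, state the peroxidase-label step it needs and its place before DAB, and add both reagents to the list.

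In the same revision, check the order of the serum block (step 4), which at present follows the primary antibody (step 3).

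Under the first option the cost is protocol wording only, with no extra samples, sections or analyses. That depends on the kit recognising rabbit IgG. The second option would also need reagents not now listed, and the documents give no basis for costing them.
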